8.1.2 OBJECTIVE EVALUATIONS

Participants will undergo the following disease rating scales and cognitive examination evaluations prior to stimulation:

- The MDS UPDRS part Ia - this is a questionnaire, administered by the investigator, and consists of 6 question, each scored 0-4 points. Score range is 0-24. It takes 10 minutes to administer⁵¹. This will be completed at the screening visit
- MDS UPDRS part III – this is the neurological examination portion of the MDS UPDRS, and takes about 10 minutes to complete⁵¹. Each question is scored 0-4. Score range is 0-132, with higher score indicating higher burden of motor symptoms. This will be completed at the screening visit
- The MDS UPDRS part IV – this is the dyskinesia rating portion. It consists of 6 questions, each scored from 0-4 points and takes 10 minutes to complete⁵¹. Score range is 0-24. This will be completed at the screening visit.

- MoCA – Montreal Cognitive Assessment. This is a neurocognitive screening tool, and takes about 15 minutes to administer⁵⁰. The visuospatial/executive function portion consists of three questions with a score range of 0-5; the naming portion consists of three questions with a score range of 0-3; the attention portion consists of 4 questions with a score range of 0-6; the abstraction portion has 2 questions and has a score range of 0-2; The delayed recall is one question and is scored 0-5 points; and orientation is 6 questions with a score range of 0-6 points. The total score range is 0-30, where lower score indicates higher burden of symptoms. This will be completed at the screening visit.
- Participants will undergo EEG before and immediately after brain stimulation. A high-density EEG net (128 electrodes including electrooculography electrodes; MagStim EGI, Inc.) and two submental electromyography (EMG) electrodes will be applied. Continuous EEG recording will be performed for 8 minutes while the participant is asked to keep their eyes open and focused on a crosshairs. Sampling rate during the continuous recording will be 1 kHz with Cz as the reference and a channel between Cz and Pz as ground, using an EGI system with SDK AmpServer Pro (Geodesic, Eugene, Oregon). EEG frequency will be reported in Hz. The primary outcome measure, FMT power, will be reported in μ .
- iTBS: Subjects will undergo iTBS to the mPFC, left DLPFC, and left S1 in a triple cross-over study design. The MagVenture MagPro X100 TMS device with active cooling coil will be used. Stimulation location will be determined using established scalp coordinates for each stimulation location with the “10-20” international coordinate system⁴²⁻⁴⁵. For the mPFC, stimulation will be done at the Fp1 EEG electrode location, which can be calculated as along the midline of the scalp and 10% of the distance from nasion to inion. For left DLPFC, stimulation will be done at the F3 location using the Beam-F3 technique^{46,47}. For the primary sensory cortex, stimulation will be done at the motor hotspot used for intensity calibration. Stimulation will be delivered at 80% active motor threshold. Accelerated iTBS will be performed in the reclining position to reduce symptoms of orthostatic hypotension, with subjects awake and at rest. Subjects will receive bursts of 3 pulses at 50 Hz repeated at 200-msec intervals (5Hz) for two seconds^{48,49}. The two-second trains will be repeated 20 times every 10 seconds (4 minutes total stimulation time), and followed by a 20 minute rest period. This sequence will be repeated 4 times. Behavioral effects of stimulation last at least 36 hours after one stimulation session with this protocol¹.

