4.2 SCIENTIFIC RATIONALE FOR STUDY DESIGN

The stimulation locations in the current study design were chosen due to prior data implicating the medial prefrontal cortex and dorsolateral prefrontal cortex in both autonomic and affective disorders. Primary sensory cortex was chosen as a control site due to its limited involvement in Parkinson's disease pathology, autonomic function, and depression. We chose a control stimulation location rather than sham stimulation because participants will be able to feel the difference between real and sham stimulation in this crossover design. A triple crossover design was chosen to maximize study recruitment and minimize subject variability between stimulation arms.

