4.3 JUSTIFICATION FOR DOSE

Transcranial magnetic stimulation (TMS) is a safe, non-invasive tool routinely used in clinical care which applies magnetic fields to the brain using coils placed on the scalp. During the first stimulation session in the study, participants will receive a motor thresholding procedure in which electrodes are attached to

the first dorsal interosseous muscle of the right hand, or another muscle on the hand or arm that is accessible to be targeted by TMS to the motor cortex. The contralateral motor cortex will be targeted by single pulses of TMS with increased stimulator output until a motor evoked potential (MEP), defined as a near-instantaneous increase in muscle activity greater than 200 microvolts, is generated. Next, the intensity of single pulse TMS will be lowered until a MEP is generated on five out of 10 pulses. This is defined as the individual's motor threshold. If MEP determination of motor threshold is not possible, the researcher will use visible twitches as a proxy for MEP. Participants will receive iTBS at 80% of their motor threshold.

Subjects will undergo iTBS to the mPFC, left DLPFC, and left primary sensory area in a triple cross-over study design. I will use a MagVenture MagPro X100 TMS device with active cooling coil. Stimulation location will be determined using established scalp coordinates for each stimulation location with the "10-20" international coordinate system ⁴²⁻⁴⁵. For the mPFC, stimulation will be done between the Fpz and Cz EEG electrode location. For left DLPFC, stimulation will be done at the F3 location using the Beam-F3 technique^{46,47}. For the primary sensory cortex, stimulation will be done 1.5cm posterior to the motor hotspot and at vertex position used for intensity calibration. Accelerated iTBS will be performed in the reclined position to reduce symptoms of orthostatic hypotension, with subjects awake and at rest. Subjects will receive bursts of 3 pulses at 50 Hz repeated at 200-msec intervals (5Hz) for two seconds^{48,49}. The two-second trains will be repeated 20 times every 10 seconds (3:30 total stimulation time), and followed by a rest period. This sequence may be repeated up to 4 times. Behavioral effects of stimulation last at least 36 hours after one stimulation session with this protocol¹.

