Clinical Evaluations: The SCOPA-AUT⁵², a validated questionnaire for autonomic symptoms in PD, and the Orthostatic Hypotension Questionnaire (OHQ)⁵³, a validated questionnaire for symptoms of orthostatic

intolerance, will be administered before, and then by telephone one day after, and four days after each stimulation session. The Beck Depression inventory II (BDI-II)⁵⁴, recommended for screening and assessment of depression severity in PD⁵⁵, will be administered before, and then by telephone one day after, and four days after each stimulation. A trained research team member will administer the Movement Disorders Society Unified Parkinson Disease Rating Scale (MDS-UPDRS)⁵¹, a validated rating scale of PD symptom severity, at baseline. Participants will have orthostatic blood pressure measurement with a standard sphygmomanometer cuff before and after each stimulation session. All evaluations will be done with subjects in the “on” medication state with regards to dopaminergic medication dosing. Quantitative EEG (qEEG) recordings will be done before and immediately after each stimulation session. EEG: A high-density EEG net (128 electrodes including electrooculography electrodes; MagStim EGI, Inc.) and two submental electromyography (EMG) electrodes will be applied. Continuous qEEG recording will be performed for 8 minutes while the participant is asked to keep their eyes open and focused on a crosshairs. Sampling rate during the continuous recording will be 1 kHz with Cz as the reference and a channel between Cz and Pz as ground, using an EGI system with SDK AmpServer Pro (Geodesic, Eugene, Oregon). Intermittent theta-burst stimulation: Subjects will undergo iTBS to the mPFC, left DLPFC, and left primary sensory area in a triple cross-over study design. I will use a MagVenture MagPro X100 TMS device with active cooling coil. Stimulation location will be determined using established scalp coordinates for each stimulation location with the “10-20” international coordinate system⁴²⁻⁴⁵. For the mPFC, stimulation will be done at the Fp1 EEG electrode location, which can be calculated as along the midline of the scalp and 10% of the distance from nasion to inion. For left DLPFC, stimulation will be done at the F3 location using the Beam-F3 technique^{46,47}. For the primary sensory cortex, stimulation will be done 1.5cm posterior to the motor hotspot used for intensity calibration. Stimulation will be delivered at 80% active motor threshold. Accelerated iTBS will be performed in the reclined position to reduce symptoms of orthostatic hypotension, with subjects awake and at rest. Subjects will receive bursts of 3 pulses at 50 Hz repeated at 200-msec intervals (5Hz) for two seconds^{48,49}. The two-second trains will be repeated 20 times every 10 seconds (4 minutes total stimulation time), and followed by a 20 minute rest period. This sequence will be repeated 4 times. Behavioral effects of stimulation last at least 36 hours after one stimulation session with this protocol¹. TMS is FDA-approved for the treatment of symptoms of depression, and is a widely-used safe clinical tool.

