
6.1.3 DOSING AND ADMINISTRATION

During the first stimulation session in the study, participants will receive a motor thresholding procedure in which electrodes are attached to the first dorsal interosseous muscle of the right hand, or another muscle on the hand or arm that is accessible to be targeted by TMS to the motor cortex. The contralateral motor cortex will be targeted by single pulses of TMS with increased stimulator output until a motor evoked potential (MEP), defined as a near-instantaneous increase in muscle activity greater than 200 microvolts, is generated. Next, the intensity of single pulse TMS will be lowered until a MEP is generated on five out of 10 pulses. This is defined as the individual’s motor threshold. If MEP determination of motor threshold is not possible, the researcher will use visible twitches as a proxy for MEP. Participants will receive iTBS at 80% of their motor threshold.

Subjects will undergo iTBS to the mPFC, left DLPFC, and left primary sensory area in a triple cross-over study design. I will use a MagVenture MagPro X100 TMS device with active cooling coil. Stimulation

location will be determined using established scalp coordinates for each stimulation location with the “10-20” international coordinate system⁴²⁻⁴⁵. For the mPFC, stimulation will be done at the Fp1 EEG electrode location, which can be calculated as along the midline of the scalp and 10% of the distance from nasion to inion. For left DLPFC, stimulation will be done at the F3 location using the Beam-F3 technique^{46,47}. For the primary sensory cortex, stimulation will be done 1.5cm posterior to the motor hotspot used for intensity calibration. Accelerated iTBS will be performed in the reclined position to reduce symptoms of orthostatic hypotension, with subjects awake and at rest. Subjects will receive bursts of 3 pulses at 50 Hz repeated at 200-msec intervals (5Hz) for two seconds^{48,49}. The two-second trains will be repeated 20 times every 10 seconds (4 minutes total stimulation time), and followed by a 20 minute rest period. This sequence will be repeated 4 times. Behavioral effects of stimulation last at least 36 hours after one stimulation session with this protocol¹.

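### The iTBS delivery instructions conflict on the S1 control and mPFC targets, two of the three location levels in the Aim 1 model

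*Combined protocol and SAP*

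**What the plan says.** Four sections describe stimulation delivery: 4.3 (Justification for Dose), 6.1.2 (Study Intervention Description), 6.1.3 (Dosing and Administration) and 8.1.2 (Objective Evaluations).

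**S1.** Section 8.1.2 reads "For the primary sensory cortex, stimulation will be done at the motor hotspot used for intensity calibration". The same bullet names the intended target: "Subjects will undergo iTBS to the mPFC, left DLPFC, and left S1 in a triple cross-over study design". Section 6.1.2 reads "For the primary sensory cortex, stimulation will be done 1.5cm posterior to the motor hotspot used for intensity calibration", and 6.1.3 uses the same wording. Section 4.3 has "stimulation will be done 1.5cm posterior to the motor hotspot and at vertex position used for intensity calibration".

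**mPFC.** Section 4.3 reads "For the mPFC, stimulation will be done between the Fpz and Cz EEG electrode location". Section 6.1.3 has "stimulation will be done at the Fp1 EEG electrode location, which can be calculated as along the midline of the scalp" and puts the point at 10% of the nasion-inion distance; 6.1.2 and 8.1.2 agree. The abbreviation list in 10.3 defines Fp1 as a left anterior prefrontal electrode.

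**DLPFC.** All four sections give F3, located by the Beam-F3 method.

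**Dose.** Sections 6.1.2, 6.1.3 and 8.1.2 fix 4 sequences with a 20-minute rest. Section 4.3 permits up to 4 and does not state the length of the rest.

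**Why S1.** Section 4.2 gives the rationale: "Primary sensory cortex was chosen as a control site due to its limited involvement in Parkinson's disease pathology, autonomic function, and depression". Section 9.4.1 models FMT power on stimulation location (mPFC, DLPFC, S1), time, and their interaction.

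**The concern.** Stimulation site is what is randomised in this trial, and it is the factor that carries the Aim 1 hypothesis. An operator who followed 8.1.2 to the letter would deliver the control condition to the motor-cortex site used for thresholding. Section 4.2 argues for primary sensory cortex and says nothing in support of motor cortex as a control in Parkinson's disease. The experimental level has a similar problem: a span and a point are different instructions, and the label on the point contradicts its own description.

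Other parts of the protocol do not resolve this. Section 6.1.1.2 documents operator training but gives no coordinates. The randomisation in 6.2 assigns site names only. Section 10.1.8 states that there is no site monitoring plan. Section 10.1.11 defines a deviation as noncompliance with the protocol, so a coil placed at either S1 position would comply with one section and breach another.

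**Working it through.** The check is mainly a side-by-side reading of the four descriptions.

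| Item | 4.3 | 6.1.2 | 6.1.3 | 8.1.2 |
|---|---|---|---|---|
| S1 | 1.5 cm behind motor hotspot, plus a vertex reference | 1.5 cm behind hotspot | 1.5 cm behind hotspot | at the hotspot |
| mPFC | span, Fpz to Cz | midline, 10% point, labelled Fp1 | same as 6.1.2 | same as 6.1.2 |
| DLPFC | F3 (Beam-F3) | F3 (Beam-F3) | F3 (Beam-F3) | F3 (Beam-F3) |
| Sequences | up to 4 | 4 | 4 | 4 |
| Rest | length not stated | 20 min | 20 min | 20 min |
| Stated time per sequence | 3:30 | 4 min | 4 min | 4 min |
| Threshold (80% of) | type not stated | active | type not stated | active |

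1. **Distinct targets.** S1 has three, mPFC has two and DLPFC has one. Two of the three location levels conflict.

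2. **What the hotspot is.** Sections 4.3 and 6.1.3 describe thresholding by single pulses over the contralateral motor cortex until a muscle response is evoked. Read literally, 8.1.2 therefore targets motor cortex, against the S1 label in its own bullet.

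3. **Where the sections agree.** Sections 6.1.2 and 6.1.3 match on all three targets, the sequence count and the rest. Section 8.1.2 departs from them only on S1. Section 4.3 departs on S1, mPFC, sequence count, rest and total time together.

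4. **Pulses.** A burst has 3 pulses. A train has 5 Hz × 2 s = 10 bursts. A sequence has 20 trains. Pulses per sequence: 3 × 10 × 20 = 600.
   - If 4 means four runs in total, the fixed dose is 4 × 600 = 2400. The 4.3 wording then permits 600, 1200, 1800 or 2400, which is 25%, 50%, 75% or 100% of that.
   - If 4 means repeats after a first run, the fixed dose is 5 × 600 = 3000. The 4.3 wording then permits 600 to 3000, or 20% to 100%.

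5. **Timing.** With trains starting every 10 s, a sequence lasts 19 × 10 + 2 = 192 s, or 200 s counting the last interval. With 10-s gaps between trains it lasts 20 × 2 + 19 × 10 = 230 s, or 240 s counting the last gap. The stated 4 minutes (240 s) fits the second reading; the stated 3:30 (210 s) fits neither. The pulse count is 600 in every case, so this is clean-up only.

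6. **Power.** Section 9.2 states power of 0.82 for N = 45, f² = 0.15, α = 0.05 and three predictors. With noncentrality 0.15 × 45 = 6.75 and 45 − 3 − 1 = 41 error degrees of freedom, a one-sided test of a single coefficient gives 0.819, which reproduces it. Coil position is not an input, so the conflict does not change this figure.

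**The case against.** The strongest reply is that the sections an operator would consult, 6.1.2 and 6.1.3, agree fully on targets and dose. The outliers are a rationale section and a list of assessments. The 8.1.2 sentence is the 6.1.3 sentence without its offset, in a bullet that names left S1, and the rest of the protocol names S1 or primary sensory cortex throughout. For mPFC, the 10% midline rule shows the intended point despite the wrong label. This is one site with trained operators, and nothing shows that delivery varied.

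Most of that stands. It makes a drafting slip in 8.1.2 the likeliest explanation and limits what can be claimed. It does not remove the conflict, because nothing makes section 6 govern.

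A reader might infer four stronger things that the documents do not support:

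- **That the control was delivered over motor cortex, or that Aim 1 is biased.** No document records what was delivered, and none gives coil focality from which the consequence of 1.5 cm for FMT could be judged. The comparison of mPFC with DLPFC does not depend on the S1 wording at all.
- **That the majority text is correct.** Sections 6.1.2, 6.1.3 and 8.1.2 are near copies, so their agreement is not independent confirmation. Section 4.3 differs on several items at once and could be a later revision that was not carried through. The amendment history shows no entries in the available text, which settles nothing either way.
- **That 4.3 supports the 6.1.2 and 6.1.3 S1 target without qualification.** It shares the offset but adds the vertex reference.
- **That dose varied fourfold.** The 25% figure is the arithmetic extreme of a permissive phrase. No section plans a one-sequence visit or lets dose differ by location.

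**Conclusion.** The concern holds as an internal inconsistency in how the intervention is specified. Two of the three Aim 1 location levels, one experimental and one control, are not tied to one definition across the protocol, and the dose is fixed in three sections but open in one. Followed literally, 8.1.2 delivers a control that 4.2 does not justify.

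Confidence is high in the textual conflict and extends no further. The documents do not show which text was used, the effect on the location-by-time estimate cannot be calculated from them, and no loss of power is demonstrated. The pulse range rests on the stated burst and train parameters and on how the number 4 is counted. This should be fixed, but it is not shown to invalidate the primary analysis.

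**What to change.** 1. Make 6.1.3 the single governing specification, and have 4.3, 6.1.2 and 8.1.2 refer to it.
2. Restore the 1.5 cm posterior offset for S1 in 8.1.2, to match 6.1.2 and 6.1.3. Explain or delete the vertex reference in 4.3.
3. Have the investigators confirm one midline mPFC point, and correct the Fp1 label.
4. Have them state whether 4.3 is a later revision. Then fix one sequence count and rest period for every visit, subject to the discomfort stopping rule in 2.3.1 and 8.2, and say whether the count is total runs or repeats.
5. Log coil position and pulses delivered at each visit. For anyone already stimulated, record which target was used, or that it is unknown.
6. Run a sensitivity analysis of the Aim 1 model only if the records show mixed targets. Define off-target against the confirmed specification, and set the rule for unknown visits beforehand. Dropping visits would disturb the counterbalancing of the six orders in 6.2, so this should not replace the primary analysis.
7. As clean-up, state the train spacing and total time once, and say whether the threshold is active or resting.

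The cost is one amendment, which under the Statement of Compliance needs IRB approval before use, and a short log entry per visit. If stimulation has begun, add a one-time check of session records and possibly one further model run. No extra visits or participant procedures are needed.

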8.2 SAFETY AND OTHER ASSESSMENTS

Pre-screening for the study will involve review of the medical chart for the presence of exclusionary criteria, particularly medical conditions and medications, which may put the participant at risk during the study. These criteria will also be reviewed with the participant at the screening visit and at each stimulation session prior to stimulation. Screening will be performed within 21 days of initial study stimulation visit.

Safety will be monitored throughout the study. A stimulation adverse effects questionnaire will be used based on common side effects experienced with TMS. This questionnaire will be administered at the end of each stimulation session. Additionally, participants will be continually asked about their comfort level during stimulation sessions. If a participant reports greater than moderate level of discomfort during stimulation, the stimulation will be immediately discontinued.

The PI will monitor the study for any adverse and serious adverse events. All serious adverse events will be reported to the IRB. Should there be a serious adverse event that occurs that increases the risks to the participants, the study will be stopped and an investigation will be conducted and a findings report generated before the study is resumed. At the time of enrollment, we will ensure we have an active and accurate phone number on file to contact the subject.

Medical follow-up

In the event that a subject is found during the course of the study to need medical or psychological follow-up related to their study involvement, the following procedures will be followed to address their issues.

Medical: For urgent issues, we will direct subjects to the nearest emergency room versus urgent care center for evaluation, based off of the described difficulties and symptoms. For nonurgent (subacute, chronic) issues related to neurologic condition, a follow-up appointment within our department will be scheduled for within 72 hours of the communication. If the issue is unrelated to their movement disorder but also nonurgent, we will communicate with the subject's primary care physician and, when appropriate, disclose necessary information regarding the study protocol should it be relevant to the complaints at hand.

Psychological: for urgent issues, we will direct subjects to the nearest crisis unit if necessary (including but not limited to suicidal ideations or intentions, severe and rapid depression/anxiety). For nonurgent (subacute/chronic) issues, will supply patient with local mental health care specialists near them as well as contact information for those within the university system to obtain the next available appointment.

The burden of cost of all medical care for conditions which arise in the course of participation in the study will on the subject. In case symptoms occur outside of business hours, the subjects will be provided the telephone number of the hospital page operator and the operator will be asked to page the PI directly. For non-urgent issues, the subjects will be asked to call [name] office number or the research assistant's phone number which are listed on the consent form of which the subject will receive a copy. For urgent or emergent issues, the subjects will be instructed to present to their nearest emergency room.

